8.4 Pharmacokinetic Analyses

BEGEDINA concentrations will be evaluated using Nonlinear Mixed Effects Modeling (NONMEM®) to construct a Population Pharmacokinetic (PK) model. The model will be used to assess the significance of various covariates on PK of BEGEDINA, e.g., patient age, gender, body weight, renal function and relevant laboratory parameters.

8.5 Health Outcomes Analyses

The subject's QoL data will be summarized using descriptive statistics.

8.6 Interim Analyses

One unblinded interim analysis is planned when Day 28 response data is available for approximately 50% of the subjects. This analysis will be conducted by an independent, unblinded statistician and statistical programmer and results will be reviewed by the DSMB (see Section 6.2.6).

Two objectives are associated with this interim analysis:

- A non-binding futility analysis for which the conditional power will be calculated given the unblinded interim results with future projection under the observed trend as well as other more optimistic or skeptical assumptions for the future data. If the resulting conditional power is deemed to be too low, the study can be considered to be stopped. Since there is no possibility to stop for superiority, there will be no adjustment to the final significance level. If interim results for response at Study Day 28 is very convincing (i.e., with a one-sided p-value less than 0.001), the DSMB may recommend

that an independent unblinded team (excluding the sponsor/CRO study specific team) submit the interim results to Health Authorities for conditional approval. The study will be continued as planned in order to determine the final results for response at Study Day 28, the results for TRM, overall survival, other secondary efficacy endpoints and safety. Since there is no possibility to stop for superiority, there will be no adjustment to the final significance level for response at Study Day 28 (as only the final results will be relevant for unconditional approval).

9.0 ETHICS

9.1 Institutional Review Board (IRB) or Independent Ethics Committee (IEC)

An Ethics Committee should approve the final protocol, including the final version of the Informed Consent Form (ICF) and any other written information and/or materials to be provided to the subjects. The investigator will provide the Sponsor or the CRO with documentation of IRB/IEC approval of the protocol and informed consent before the study may begin at the study center(s). The investigator should submit the written approval to the Sponsor or representative before enrolment of any subject into the study.

The Sponsor or representative should approve any modifications to the ICF that are needed to meet local requirements.

The investigator will supply documentation to the CRO of required IRB/IEC's annual renewal of the protocol, and any approvals of revisions to the informed consent document or amendments to the protocol.

The Sponsor or representative will report promptly to the IRB/IEC, any new information that may adversely affect the safety of subjects or the conduct of the study. Similarly, the Sponsor or representative will submit written summaries of the study status to the IRB/IEC annually, or more frequently if requested by the IRB/IEC. Upon completion of the study, the Sponsor (or delegated CRO) will provide the Ethics Committee with a brief report of the outcome of the study, if required.

The Sponsor or representative will handle the distribution of any of these documents to the national Regulatory Authorities.

The Sponsor or representative will provide Regulatory Authorities, Ethics Committees and Investigators with safety updates/reports according to local requirements, including Suspected Unexpected Serious Adverse Reactions, where relevant.

Each investigator is responsible for providing the IRB/IEC with reports of any serious and unexpected ADRs from any other study conducted with the study drug. The Sponsor or representative will provide this information to the investigator so that he/she can meet these reporting requirements.

9.2 Ethical Conduct of the Study

This study will be conducted and the informed consent will be obtained according to the ethical principles stated in the Declaration of Helsinki (52nd General Assembly, Edinburgh, Scotland, October 2000), the applicable guidelines for GCP (CPMP/ICH/135/95), or the applicable drug and data protection laws and regulations of the countries where the study will be conducted.

GCP is an international ethical and scientific quality standard for designing, conducting, recording and reporting studies that involve the participation of human subjects. The study will be conducted in compliance with GCP and the applicable national regulations so as to assure that the rights, safety and well-being of the participating study subjects are protected consistent with the ethical principles that have their origin in the Declaration of Helsinki.

9.3 Subject Information and Informed Consent

The ICF will be used to explain the risks and benefits of study participation to the subject in simple terms before the subject will be entered into the study. The ICF contains a statement that the consent is freely given, that the subject is aware of the risks and benefits of entering the study, and that the subject is free to withdraw from the study at any time. Written consent must be given by the subject and/or legal representative, after the receipt of detailed information on the study.

The investigator is responsible for ensuring that informed consent is obtained from each subject or legal representative and for obtaining the appropriate signatures and dates on the informed consent document prior to the performance of any protocol procedures and prior to the administration of study medication. The investigator will provide each subject with a copy of the signed and dated consent form.

10.0 STUDY ADMINISTRATION

10.1 Data Handling and Record Keeping

It is the investigator's responsibility to maintain essential study documents (protocol and protocol amendments, completed eCRFs, signed ICFs, relevant correspondence, and all other supporting documentation). The study site should plan on retaining such documents for approximately 15 years after study completion. The study site should retain such documents until at least 2 years after the last approval of a marketing application in an ICH region and until there are no pending or contemplated marketing applications in an ICH region or at least 2 years after the formal discontinuation of clinical development of the investigational product. These documents should be retained for a longer period if required by the applicable regulatory requirements or the hospital, institution, or private practice in which the study is being conducted. Subject identification codes (subject names and corresponding study numbers) will be retained for this same period of time. These documents may be transferred to another responsible party, acceptable to Sponsor, who agrees to abide by the retention policies. Written notification of transfer must be submitted to Sponsor. The investigator must contact the Sponsor prior to disposing of any study records.

The US FDA regulations (21 CFR §312.62[c]) and the ICH Guideline for GCP (see Section 4.9 of the guideline) require that records and documents pertaining to the conduct of this study and the distribution of study drug, including eCRFs, consent forms, laboratory test results, and medication inventory records, must be retained by the Principal Investigator for 15 years after the last marketing application approval in an ICH region or after at least 15 years have elapsed since formal discontinuation of clinical development of the investigational. The Sponsor will notify the Principal Investigator of these events.

No records should be disposed of without the written approval of the Sponsor.

For studies conducted outside the United States under a U.S. IND, the Principal Investigator must comply with U.S. FDA IND regulations and with those of the relevant national and local health authorities.

10.2 Direct Access to Source Data/Documents

The investigator will prepare and maintain adequate and accurate source documents to record all observations and other pertinent data for each subject randomized into the study.

The investigator will allow the Sponsor, the delegated CRO, and authorized Regulatory Authorities to have direct access to all documents pertaining to the study, including individual subject medical records, as appropriate.

10.3 Investigator Information

10.3.1 Investigator Obligations

This study will be conducted in accordance with the ICH Harmonized Tripartite Guideline for GCP (GCP, 1997), the US CFR Title 21 parts 50, 56, and 312; and European Legislation; and the ethical principles that have their origin in the Declaration of Helsinki.

A summary of Investigator Obligations is provided in Appendix 5 (see [Section 12.5](#)).

The investigator agrees to conduct the clinical study in compliance with this protocol after the approval of the protocol by the IEC/IRB in compliance with local regulatory requirements. The Investigator and the Sponsor will sign the protocol to confirm this agreement.

10.3.2 Protocol Signatures

After reading the protocol, each investigator will sign the protocol signature page and send a copy of the signed page to the Sponsor or representative (Appendix 6, see Section 12.6). By signing the protocol, the investigator confirms in writing that he/she has read, understands and will strictly adhere to the study protocol and will conduct the study in accordance with ICH Tripartite Guidelines for GCP and applicable regulatory requirements. The study will not be able to start at any center where the investigator has not signed the protocol.

10.3.3 Publication Policy

The data generated by this study are confidential information of the Sponsor. The Sponsor will make the results of the study publicly available. The publication policy with respect to the investigator and study center will be set forth in the Clinical Trial Agreement.

10.4 Financing and Insurance

Sponsor will provide insurance in accordance with local guidelines and requirements as a minimum for the subjects participating in this study. The terms of the insurance will be kept in the study files.

12.0 APPENDICES

12.1 Appendix 1: Recommendations for Steroid Taper

Table 25 Recommendations for a Steroid Taper (Intravenous Methylprednisolone)

Dose of intravenous methylprednisolone	Day of taper
2 mg/kg/day divided into 2-3 doses	Days 0-6
2 mg/kg/day, once daily	Days 7-13
1.5 mg/kg/day	Days 14-21
1.0 mg/kg/day	Days 21-28
0.5 mg/kg/day	Days 29-35
0.4 mg/kg/day	Days 36-42
0.3 mg/kg/day	Days 43-49
0.2 mg/kg/day	Days 50-56
0.1 mg/kg/day	Days 57-63
0.1 mg/kg/day every other day	Days 63-69
Discontinue	Day 70

12.2 Appendix 2: Karnofsky Performance Status

	Karnofsky Performance Status scale ≥ 16 yrs.
100%	Normal, no complaints, no evidence of disease
90%	Able to carry on normal activity, minor signs or symptoms of disease
80%	Normal activity with effort, some signs or symptoms of disease
70%	Cares for self, unable to carry on normal activity or to do active work
60%	Requires occasional assistance from others but able to care for most needs
50%	Requires considerable assistance from others and frequent medical care
40%	Disabled, requires special care and assistance
30%	Severely disabled, hospitalization indicated, death not imminent
20%	Very sick, hospitalization necessary, active support, treatment necessary
10%	Moribund, fatal process progressing rapidly

12.3 Appendix 3: Short Form 36

Short Form (36) Health Survey

This survey was reprinted with permission from the RAND Corporation. Copyright © the RAND Corporation. RAND's permission to reproduce the survey is not an endorsement of the products, services, or other uses in which the survey appears or is applied.

The SF-36 is reproduced here (in part or in its entirety) with permission from the RAND Corporation. Copyright © the RAND Corporation. RAND's permission to reproduce the survey is not an endorsement of the products, services, or other uses in which the survey appears or is applied.

Hays, RD (1994). The *Medical Outcomes Study (MOS) Measures of Patient Adherence*. Retrieved April 19, 2004, from the RAND Corporation web site:
<http://www.rand.org/health/surveys/MOS.adherence.measures.pdf>.

Short Form (36) Health Survey

1. In general, would you say your health is:	Excellent	Very Good	Good	Fair	Poor
	[1]	[2]	[3]	[4]	[5]

2. Compared to one year ago , how would you rate your health in general now ?	Much better now than one year ago	Somewhat better now than one year ago	About the same	Somewhat worse now than one year ago	Much worse now than one year ago
	[1]	[2]	[3]	[4]	[5]

The following items are about activities you might do during a typical day. Does your health now limit you in these activities? If so, how much?			
(Circle One Number on Each Line)	Yes, Limited a Lot	Yes, Limited a Little	No, Not limited at All
3. Vigorous activities , such as running, lifting heavy objects, participating in strenuous sports	[1]	[2]	[3]
4. Moderate activities , such as moving a table, pushing a vacuum cleaner, bowling, or playing golf	[1]	[2]	[3]
5. Lifting or carrying groceries	[1]	[2]	[3]
6. Climbing several flights of stairs	[1]	[2]	[3]
7. Climbing one flight of stairs	[1]	[2]	[3]
8. Bending, kneeling, or stooping	[1]	[2]	[3]
9. Walking more than a mile	[1]	[2]	[3]
10. Walking several blocks	[1]	[2]	[3]
11. Walking one block	[1]	[2]	[3]

12. Bathing or dressing yourself	[1]	[2]	[3]
----------------------------------	-----	-----	-----

During the past 4 weeks , have you had any of the following problems with your work or other regular daily activities as a result of your physical health ?		
(Circle One Number on Each Line)	Yes	No
13. Cut down the amount of time you spent on work or other activities	[1]	[2]
14. Accomplished less than you would like	[1]	[2]
15. Were limited in the kind of work or other activities	[1]	[2]
16. Had difficulty performing the work or other activities (for example, it took extra effort)	[1]	[2]

During the past 4 weeks , have you had any of the following problems with your work or other regular daily activities as a result of any emotional problems (such as feeling depressed or anxious)?		
(Circle One Number on Each Line)	Yes	No
17. Cut down the amount of time you spent on work or other activities	[1]	[2]
18. Accomplished less than you would like	[1]	[2]
19. Didn't do work or other activities as carefully as usual	[1]	[2]

20. During the past 4 weeks , to what extent has your physical health or emotional problems interfered with your normal social activities with family, friends, neighbors, or groups?	Not at all	Slightly	Moderately	Quite a bit	Extremely
	[1]	[2]	[3]	[4]	[5]

21. How much bodily pain have you had during the past 4 weeks ?	None	Very mild	Mild	Moderate	Severe	Very Severe
	[1]	[2]	[3]	[4]	[5]	[6]

22. During the past 4 weeks , how much did pain interfere with your normal work (including both work outside the home and housework)?	Not at all [1]	Slightly [2]	Moderately [3]	Quite a bit [4]	Extremely [5]	

These questions are about how you feel and how things have been with you during the past 4 weeks. For each question, please give the one answer that comes closest to the way you have been feeling.
 
How much of the time during the past 4 weeks...
						
(Circle One Number on Each Line)	All of the Time	Most of the Time	A Good Bit of the Time	Some of the Time	A Little of the Time	None of the Time
23. Did you feel full of pep?	[1]	[2]	[3]	[4]	[5]	[6]
24. Have you been a very nervous person?	[1]	[2]	[3]	[4]	[5]	[6]
25. Have you felt so down in the dumps that nothing could cheer you up?	[1]	[2]	[3]	[4]	[5]	[6]
26. Have you felt calm and peaceful?	[1]	[2]	[3]	[4]	[5]	[6]
27. Did you have a lot of energy?	[1]	[2]	[3]	[4]	[5]	[6]
28. Have you felt downhearted and blue?	[1]	[2]	[3]	[4]	[5]	[6]
29. Did you feel worn out?	[1]	[2]	[3]	[4]	[5]	[6]
30. Have you been a happy person?	[1]	[2]	[3]	[4]	[5]	[6]
31. Did you feel tired?	[1]	[2]	[3]	[4]	[5]	[6]

32. During the past 4 weeks , how much of the time has your physical health or emotional problems interfered with your social activities (like visiting with friends, relatives, etc.)?	All of the time	Most of the time	Some of the time	A little of the time	None of the time
	[1]	[2]	[3]	[4]	[5]
(Circle One Number)					
How TRUE or FALSE is each of the following statements for you.					
(Circle One Number on Each Line)	Definitely True	Mostly True	Don't not Know	Mostly False	Definitely False
33. I seem to get sick a little easier than other people	[1]	[2]	[3]	[4]	[5]
34. I am as healthy as anybody I know	[1]	[2]	[3]	[4]	[5]
35. I expect my health to get worse	[1]	[2]	[3]	[4]	[5]
36. My health is excellent	[1]	[2]	[3]	[4]	[5]

12.4 Appendix 4: ECOG Performance Scale

Developed by the Eastern Cooperative Oncology Group, [name], Group Chair.*

GRADE	ECOG PERFORMANCE STATUS
0	Fully active, able to carry on all pre-disease performance without restriction
1	Restricted in physically strenuous activity but ambulatory and able to carry out work of a light or sedentary nature, e.g., light house work, office work
2	Ambulatory and capable of all self-care but unable to carry out any work activities; up and about more than 50% of waking hours
3	Capable of only limited self-care; confined to bed or chair more than 50% of waking hours
4	Completely disabled; cannot carry on any self-care; totally confined to bed or chair
5	Dead

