4.3.3 Rationale for Choice of Outcome Variables

Very few prospective studies have evaluated the efficacy and safety of second-line therapy for acute GvHD, and interpretation of these studies is made difficult due to the lack of standardization (Qian et al., 2013). Response rates and OS have frequently been used as the endpoints in these trials (Martin et al., 2012). For example, in a study investigating the

efficacy of the monoclonal antibody daclizumab as treatment for acute GvHD, response at Study Day 43 was the primary endpoint of the study. Survival was a secondary endpoint and was scored on Study Day 120 (Przepiorka et al., 2000).

However, in this current study, the selection of Study Day 28 post-treatment as the timepoint for assessing short-term response to treatment is consistent with other trials that have investigated the endpoints for acute GvHD treatment (Inamoto et al., 2014; Levine et al., 2010; MacMillan et al., 2010; Saliba et al., 2012).

Overall response to treatment is based on a change from baseline in the severity of the disease. The most commonly used grading system for severity of acute GvHD is the Glucksberg system (Grades I to IV), originally published in 1974. Although the system is still widely used and has recognized prognostic value, it is complex and relies on a combination of objective assessment of organ function (or organ-disease involvement) and subjective assessment of performance status (Glucksberg et al., 1974, Przepiorka et al., 1995). An alternative to this system is the International Bone Marrow Transplant Registry (IBMTR) index, which uses the same organ staging system, but is independent of performance status, which is sometimes difficult to document (Cahn et al., 2005; Rowlings et al., 1997). This system has been validated and is the grading system (Grades A, B, C and D) used in the current study for the assessment of this primary endpoint.

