6.1.1.1.1 Grading the Severity of Acute GvHD

At the visits presented in Table 19, the severity of the subject's GvHD will be graded using the IBMTR system (see Table 21) and the Glucksberg criteria (see Table 23).

GvHD will be graded and documented by stage of each organ, with date of onset/change in stage; gut GvHD will be documented as upper GI tract (limited to anorexia, nausea, vomiting) and/or lower GI tract. This will permit also an exploratory analysis of refined response by standard-risk or high-risk GvHD at onset, in which standard risk is defined by single organ involvement (stage 1 to 3 skin or stage 1 to 2 GI) or 2 organ involvement (stage 1 to 3 skin plus stage 1 GI or stage 1 to 3 skin plus stage 1 to 4 liver), and high-risk are those which are not standard risk ([MacMillan et al., 2015](#)).

The IBMTR

For the analysis of the primary endpoint, severity of acute GvHD will be graded using the IBMTR system. In this system, severity is determined by a clinical assessment of the degree of involvement of the skin, liver and GI tract (Table 21). Grade A GvHD is characterized as mild disease, Grade B GvHD as moderate, Grade C as severe and Grade D life-threatening ([Cahn et al., 2005](#); [Przepiorka et al., 1995](#); [Rowlings et al., 1997](#)).

Table 21 Grading of Graft-versus-Host Disease According to the IBMTR System

Grade	Category	Skin	Intestine	Liver
A	Mild	1	0	0
B	Moderate	2	0	0
		0-2	1	0-1
		0-2	0-1	1
		0-2	2	0-2
		0-2	0-2	2
C	Severe	3	1	0-1
		3	0-1	1
		3	0	0
		0-3	0-3	2-3
		3	0-2	0-3
D	Life-threatening	0-3	0-3	4
		0-3	4	0-4
		4	0-4	0-4

The maximum possible grading should be selected. The highest organ stage determines the grade.
 Reference: [Cahn et al., 2005](#); [Rowlings et al., 1997](#).

Glucksberg Criteria

An overall grade for acute GvHD is obtained by first assigning a stage for each of the 3 target organs (skin, liver gut). Staging of each organ, a clinical assessment, is summarized in Table 22.

With the Glucksberg approach to grading the severity of acute GvHD, this organ staging is then combined with a functional performance status assessment, using the Eastern

Cooperative Oncology Group performance status measure, to assign an overall grade for acute GvHD, according to Glucksberg and as presented in Table 23.

Table 22 Staging of Graft-versus-Host Disease (Glucksberg Criteria)

Stage	Skin	Liver	Gastro-enteric Tract

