6.1.2.6 Change from Baseline in Karnofsky Performance Status

The Karnofsky Performance Status scale allows subjects to be classified according to their functional impairment.

The change from baseline in the Karnofsky Performance Status scale will be derived for the timepoints noted in Table 19.

A copy of the Karnofsky Performance Status scale is provided in Appendix 2 (Section 12.2).

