8.1 Determination of Sample Size

This study will have two primary efficacy endpoints (see Section 6.1.1).

For the primary efficacy endpoint OR at Study Day 28, it is assumed that the conventional treatment would have a response rate of 50%, and further assumed that the response rate for the BEGEDINA treatment arm would be 75%. In order to have 80% power for a one-sided test at $\alpha=0.025$, 58 patients per treatment group would be required.

For the other primary endpoint, TRM up to Study Day 180, the cumulative incidence for the conventional treatment is assumed to be 50% and the one for BEGEDINA is assumed to be 30% (relative reduction by 40%). 80% power for a one-sided log-rank test with significance level 0.025 requires a total of 103 deaths without prior diagnosis of relapse. These can be expected with 92 subjects per treatment group, provided there are no early dropouts and no diagnoses of relapse. If drop-outs or diagnoses of relapse are observed during the recruitment period, the sample size may be slightly increased, e.g., to 100 subjects per treatment group. Since the required sample size for TRM is larger than the one for overall response, a total sample size of 184 (up to 200, respectively) will be used.

Overall survival up to 180 days is the key secondary endpoint and the planned sample size provides adequate power to reject the null hypothesis of equal OS, assuming 20 to 25 percent differences in survival probabilities in favor of BEGEDINA.

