8.3 Statistical Methods

Descriptive statistics [e.g., number of subjects, mean and standard deviation, median, minimum, and maximum] will be provided for continuous variables and frequency counts and percentages will be displayed for categorical variables. All outputs will be generated by study treatment group.

All statistical tests will be conducted at a one-sided significance level of 2.5% unless otherwise specified. Treatment effect estimates will be reported with two-sided 95% confidence interval (CI).

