8.3.4 Analysis of Primary Efficacy Endpoints

There are two primary efficacy endpoints as health authorities (EMA/FDA) have requested different primary endpoints: OR at Study Day 28 (see Section 6.1.1.1) is the single primary

endpoint for FDA, TRM up to Day 180 (see [Section 6.1.1.2](#)) is the single primary endpoint for EMA. The analysis methods are:

- the null hypothesis of equal OR probabilities for BEGEDINA and conventional treatment will be tested using a Cochran-Mantel-Haenszel test stratified for baseline GvHD severity grade (as used in the randomization) at the one-sided $\alpha = 0.025$ level. The treatment effect will be expressed as odds ratio with a two-sided 95% CI.
- TRM up to Study Day 180 will be graphically displayed by non-parametric cumulative incidence curve estimates. The null hypothesis of same TRM (defined as death without prior diagnosis of relapse) cumulative incidences for both study treatments will be tested by a one-sided test stratified for the baseline GvHD severity grade (as used in the randomization) taken into account the competing risk of relapse diagnosis. The one-sided significance level is set to $\alpha = 0.025$. Regression analysis of cause-specific hazards stratified for the baseline GvHD severity will be performed as supportive analysis in order to quantify the treatment effect in terms of hazard ratios and two-sided 95% CI.

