8.3.5 Analyses of Secondary Efficacy Endpoints

8.3.5.1 Analysis of Key Secondary Efficacy Endpoint

The null hypothesis of same OS curves (up to Study Day 180) for both study treatments will be tested by a one-sided log-rank test stratified for the baseline GvHD severity grade (as used in the randomization). The one-sided significance level is set to $\alpha = 0.025$. A proportional hazards regression analysis stratified for the baseline GvHD severity will be performed as supportive analysis in order to quantify the treatment effect in terms of a hazard ratio and a two-sided 95% CI. OS will be graphically displayed by Kaplan-Meier plots.

The following two sequential testing procedures will be applied to control the one-sided type-I-error probability by 0.025:

A. For the primary endpoint preferred by the FDA:

1. Test of “OR at Day 28” by a stratified Cochran-Mantel-Haenszel test with one-sided significance level 0.025
2. Only if significant, then test “OS up to Study Day 180” by a stratified log-rank test with one-sided significance level 0.025
3. Only if significant, then test “TRM up to Study Day 180” by a stratified log-rank test with one-sided significance level 0.025.

Whenever a test does not lead to rejection of a null hypothesis, the test procedure A will be stopped.

B. For the primary endpoint preferred by the EMA:

1. “TRM up to Study Day 180” by a stratified log-rank test with one-sided significance level 0.025.
2. Only if significant, then test “OR at Study Day 28” by a stratified Cochran-Mantel-Haenszel test with one-sided significance level 0.025.
3. Only if significant, then test “OS up to Study Day 180” by a stratified log-rank test with one-sided significance level 0.025

Whenever a test does not lead to rejection of a null hypothesis, the test procedure B will be stopped.

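### Baseline Karnofsky status, recorded before randomization as an entry criterion, is left out of the supportive OR, TRM and OS models; adding it is a cheap efficiency gain, not the repair of an error

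*Combined protocol and SAP*

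**What the plan says.** **Severity scales.** Section 6.1.1.1.1 describes two. For Glucksberg: "With the Glucksberg approach to grading the severity of acute GvHD, this organ staging is then combined with a functional performance status assessment". Table 23 attaches ECOG 0-1 to Grade II, 2-3 to Grade III and 3-4 to Grade IV; Appendix 4 supplies the scale, with grade 3 reading "Capable of only limited self-care; confined to bed or chair more than 50% of waking hours". For the primary endpoint the protocol uses IBMTR, "which uses the same organ staging system, but is independent of performance status" (section 4.3.3).

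**Analyses.** Sections 4.1 and 5.4 name one stratification factor, IBMTR Grade B versus C/D. The CMH test for OR, the TRM test and the OS log-rank test are stratified by that factor only. So are the two model-based analyses. For TRM: "Regression analysis of cause-specific hazards stratified for the baseline GvHD severity will be performed as supportive analysis" (8.3.4). For OS: "A proportional hazards regression analysis stratified for the baseline GvHD severity will be performed as supportive analysis" (8.3.5.1). No regression model is planned for OR.

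**Karnofsky.** Section 6.1.2.6 says: "The Karnofsky Performance Status scale allows subjects to be classified according to their functional impairment". A score of at least 50% is inclusion criterion 5. Table 19 schedules the scale at screening and at baseline, and section 4.2.2 places baseline assessments before randomization. Its only planned use is the change-from-baseline shift tables in 8.3.5.2. It is not among the baseline characteristics listed in 8.3.1.

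**The concern.** A baseline value that predicts outcome can add power when it enters the model. Here it is already collected and, being an entry condition, should be known for every randomized subject. It is also fixed before open-label assignment can influence it. The one stratifier does not carry it, because IBMTR excludes performance status.

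TRM is the single primary endpoint for the EMA, and its planned power is only 80%, on the assumption of no early dropout and no relapse. If the arms happened to differ in fitness, there would be no pre-specified adjusted estimate. One chosen after the data are seen would carry little weight, particularly in an open-label trial.

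**Working it through.** **1. The plan's own figure.** Section 8.1: OR 50% versus 75%, 80% power. Section 8.3: "All statistical tests will be conducted at a one-sided significance level of 2.5% unless otherwise specified". With pooled variance and mean rate 0.625:

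n = [1.960 × √(2 × 0.625 × 0.375) + 0.842 × √(0.5 × 0.5 + 0.75 × 0.25)]² / 0.25² = (1.342 + 0.557)² / 0.0625 ≈ 57.7, so 58 per arm. This reproduces. At the 92 per arm actually planned, OR power is 94.5%, so there is little left to gain.

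**2. TRM baseline.** Incidence of 50% versus 30% gives HR = ln 0.7 / ln 0.5 = 0.515, log HR = −0.66. Expected events are 92 × 0.5 + 92 × 0.3 = 73.6. Schoenfeld power: √73.6 / 2 × 0.664 − 1.960 = 0.89, or 81.3%. The 103 events stated in 8.1 do not follow from these incidences (Schoenfeld gives 72). That is a separate matter, and the check below uses the stated incidences.

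**3. TRM power with and without Karnofsky.** Stratified Cox model, 92 per arm, one-sided 0.025, no relapse or dropout, Karnofsky independent of grade. The documents give neither the Karnofsky distribution nor its prognostic strength, so both are assumed.

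- Simulation A (3000 runs): Karnofsky 50/60/70/80/90 in 10/20/30/25/15% of subjects (mean 71.5, SD 11.9); strata 40:60, stratum HR 1.6.
- Simulation B (2500 runs): standard normal covariate; strata 50:50, stratum log HR 0.5.

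| Assumed HR for lower Karnofsky | Unadjusted | Adjusted | Gain (points) |
|---|---|---|---|
| A: 1.0 per 10 points | 80.7% | 80.7% | 0 |
| A: 1.2 | 81.0% | 81.7% | 0.7 |
| A: 1.4 | 80.8% | 82.9% | 2.1 |
| A: 1.6 | 80.0% | 86.6% | 6.6 |
| B: 1.0 per SD | 81.3% | 81.0% | −0.3 |
| B: 1.25 | 81.7% | 82.1% | 0.4 |
| B: 1.5 | 81.5% | 84.2% | 2.7 |
| B: 2.0 | 80.1% | 88.2% | 8.1 |

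The two scales agree: 1.4 per 10 points is 1.4^1.19 ≈ 1.5 per SD. The Monte Carlo standard error of each power figure is about 0.7 to 0.8 points, so −0.3 is noise.

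**4. OR power, 92 per arm (3000 runs), CMH versus logistic with Karnofsky.** By assumed odds ratio per SD:

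- 1.0: 95.0% vs 94.7%
- 1.25: 95.1% vs 95.2%
- 1.5: 94.6% vs 95.4%
- 2.0: 94.5% vs 95.6%
- 2.5: 94.7% vs 96.8%

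**5. Where the gain comes from.** At 2.0 per SD the mean TRM log HR moves from −0.676 to −0.760, while its standard error goes from 0.244 to 0.246. The OR log odds ratio moves from 1.146 to 1.269, and its standard error rises from 0.329 to 0.352. The estimate moves; the standard error does not fall.

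**6. Validity.** With no treatment effect, the planned CMH test rejects in 2.4 to 2.6% of runs, whether or not Karnofsky is prognostic.

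**7. Chance imbalance.** The standard error of the between-arm Karnofsky difference is √(2/92) = 0.147 SD, so the 95% range is ±0.29 SD. At SD 11.9 the standard error is 1.76 points, and P(difference of at least 3 points either way) = 0.089. At HR 1.4 per 10 points, a 3-point difference moves the unadjusted log HR by 0.3 × ln 1.4 = 0.10, which is 0.10 / 0.244 ≈ 0.4 of its standard error.

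**The case against.** The strongest reply is that stratifying by the randomization factor is a coherent, pre-specified and valid analysis, and that more covariates are a matter of preference. On validity this stands in full (step 6).

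Four further points limit what can be said.

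- A reader might infer that the plan drops part of its own severity scale. It does not. Performance status belongs to Glucksberg; the scale used for stratification and response is IBMTR. Section 4.3.3 prefers it partly because performance status is hard to document, and calls that element subjective. The prognostic value it credits is that of Glucksberg as a whole. Documentation is less of an obstacle here, since entry already requires a Karnofsky score.
- A reader might infer that a chance difference in fitness biases the result. It does not: randomization and the planned confidence intervals already allow for it, and the shift in step 7 is well inside sampling error.
- The upper end of the gain needs a strong effect. An HR of 1.6 per 10 points means 1.6⁴ ≈ 6.6 times the hazard at Karnofsky 50 as at 90. The entry floor of 50% may also weaken the effect.
- Karnofsky is not the only candidate. Section 4.3.3 stresses the pattern of organ involvement, and 4.3.4 mentions age and comorbidity. The case for Karnofsky is practical: it is required at entry and is absent from the stratum by design. The sponsor could reasonably add others, if named in advance.

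Finally, section 8.0 leaves detail to a SAP whose text is not in the supplied document. That SAP may already specify adjustment, so the point covers the protocol text only.

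**Conclusion.** The point holds as an efficiency improvement. In the protocol text, no OR, TRM or OS analysis uses baseline Karnofsky, although it is recorded before randomization.

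Over the assumed range, an adjusted TRM test gains about 0 to 8 points of power and an adjusted OR test 0 to 2 points. If Karnofsky is not prognostic, nothing material is lost. OS was not simulated. These figures rest on assumed prognostic strength beyond grade, an assumed Karnofsky distribution, independence of Karnofsky and grade, and no relapse or dropout.

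Two stronger conclusions are tempting and not supported. The planned tests are not invalid or biased. Nor is precision lost in the sense of wider standard errors for the hazard or odds ratio. Because the fix keeps the adjusted models supportive, the formal power of the confirmatory tests does not change. What the trial gains is a more sensitive supportive test and an adjusted estimate fixed in advance.

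**What to change.** - **8.3.4 (TRM) and 8.3.5.1 (OS):** add the last Karnofsky value before randomization, linear per 10 points, as a covariate in the stratified cause-specific and proportional hazards regressions already planned. Report the unadjusted hazard ratios beside the adjusted ones.
- **8.3.4 (OR):** add a supportive logistic regression of Day 28 response on treatment, randomization stratum and the same Karnofsky value.
- **8.3.1:** list Karnofsky among the baseline characteristics, by arm.
- **Unchanged:** the CMH test, the stratified TRM and OS tests, both testing sequences, the strata and the endpoints. Making the adjusted tests confirmatory is not proposed, since it would replace the tests named in 8.3.5.1 and make a conditional effect the basis of the claim.

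The cost is SAP wording, one extra term in two models and one short additional model, with no new data, visits or subjects. Section 8.0 gives a natural deadline: SAP finalization before the first 30% of subjects are randomized (0.30 × 184 ≈ 55). The one downside is interpretive: adjusted hazard and odds ratios are conditional on Karnofsky and must be labelled so.
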